10.3	Investigator Documentation	96
10.4	Study Conduct.....	96
10.5	Adherence to Protocol.....	96
10.6	Adverse Events and Study Report Requirements.....	97
10.7	Investigator's Final Report.....	97
10.8	Records Retention.....	97
10.9	Publications	97
11	Study Management	98
11.1	Monitoring.....	98
11.1.1	External Data Monitoring Committee.....	98
11.1.2	Monitoring of the Study	98
11.1.3	Inspection of Records.....	98
11.2	Management of Protocol Amendments and Deviations	99
11.2.1	Modification of the Protocol.....	99
11.2.2	Protocol Deviations	99
11.3	Study Termination	99
11.4	Final Report	100
12	Reference List.....	101
13	Appendix (Israel Site-Specific Instructions).....	105

List of Tables

Table 5-2	Treatment Group Regimens	49
Table 6-1	Schedule of Activities by Clinic Visit	54
Table 6-2	Efficacy Assessments by Domain and Participant Source	67
Table 7-1	Incidence Rates and Corresponding Precision	85

List of Figures

Figure 1-1	Main Sites of Action of OV101, Benzodiazepine, and Novel Benzodiazepine-Like Compounds	33
Figure 3-1	Study Schematic.....	39

Protocol Synopsis

Protocol Number:

OV101-17-001

Title:

A Phase 2a Randomized, Double-Blind, Parallel Group, Proof-of-Concept Study Evaluating the Safety, Tolerability, and Efficacy of OV101 in Fragile X Syndrome

Sponsor:

Ovid Therapeutics Inc.
[name]
[name]

Study Phase:

Phase 2a

Study Sites:

Approximately 8 sites in the United States and approximately 1 site in Israel

Indication:

Fragile X syndrome

Rationale:

Ovid Therapeutics Inc. is developing OV101 (gaboxadol) for the treatment of rare genetic disorders that are associated with severe developmental and behavioral challenges, such as Angelman syndrome and Fragile X syndrome (FXS). Gaboxadol was initially developed for the treatment of insomnia by H. Lundbeck A/S and Merck, but its development was discontinued in 2007 for clinical and commercial reasons. Extensive nonclinical and clinical data were generated during the initial stages of development, including data from exposure to gaboxadol in more than 4300 adult subjects with insomnia and approximately 500 adult subjects in non-insomnia-related studies.

Fragile X syndrome is the most common inherited form of intellectual disability, with a prevalence of 1 in 4000 males and 1 in 8000 females. It is also the most common known genetic cause of autism; approximately 25% to 30% of individuals with FXS meet the full diagnostic criteria for autism, and approximately 5% of children with autism carry the fragile X mutation. Males with FXS have moderate to severe intellectual disability, and females with FXS range from normal to moderate impairment.

Individuals with FXS are at increased risk for a range of behavioral problems that may limit their academic performance, adaptive function, daily living skills, and social interactions. Anxiety is the most common behavioral problem in individuals with FXS, with specific symptoms of shyness, social anxiety, hyperarousal, and stereotypic behavior such as hand flapping and hand biting. Aggressive behaviors in male individuals with FXS are also common and may lead to injuries to caregivers, peers, or friends. Attention-deficit/hyperactivity disorder symptoms (overarousal, hyperactivity, distractibility, and

impulsivity) may also be noted. Individuals with FXS can experience problems in one or more of these behavior domains. There is a wide range of variability in symptoms, although they tend to be more severe in males than in females.

Current behavior therapy treatments include speech therapy, physical therapy, occupational therapy, and educational resources. Current treatments with medications target only the behavioral phenotypes and not the underlying brain deficits.

OV101 is the first highly selective, extrasynaptic gamma-aminobutyric acid (GABA) receptor agonist that binds as an orthosteric agonist to the α 4- and δ -containing subunit of extrasynaptic GABA receptors. The mechanism of action of OV101 is unique among GABAergic agents, including benzodiazepines, zolpidem and other zolpidem-like drugs, neurosteroids, and drugs that act on GABA metabolism or uptake.

The use of OV101 for treatment of individuals with FXS is based on studies in a relevant mouse model of the disease, the *Fmr1* knockout (KO) mouse, which lacks the fragile X mental retardation protein due to a disruption in its *FMR1* gene. *Fmr1* KO mice have decreased GABA synthesis, decreased presynaptic GABA release, and decreased extrasynaptic levels of GABA, resulting in decreased tonic inhibition. OV101 was shown to restore tonic inhibition in the amygdala, reduce sensory hypersensitivity and motor hyperactivity, and improve pre-pulse inhibition (signal to noise ratio) in *Fmr1* KO mice. Cogram et al recently presented data that showed full normalization of abnormal repetitive, social, and anxiety-like behaviors with OV101 in another FXS KO mouse model, the *Fmr1* KO2 mouse. Taken together, these data support the potential of OV101 to treat the core behavioral deficits noted in individuals with FXS. Importantly, the ability of OV101 to potentiate tonic inhibition is unlike any other GABAergic agent, including benzodiazepines, zolpidem, other zolpidem-like drugs, neurosteroids, and drugs that act on GABA metabolism or uptake.

Phase 2 and Phase 3 studies in adult subjects with primary insomnia demonstrated that OV101 is effective in restoring classical sleep parameters (sleep induction and sleep maintenance) and slow wave sleep, resulting in an improvement in the quality and restorative effects of sleep.

The purpose of this study is to investigate the safety, tolerability, and exploratory efficacy of treatment by oral administration of OV101 at doses of 5 mg/day (5 mg once a day [QD]), 10 mg/day (5 mg twice a day [BID]), or 15 mg/day (5 mg three times a day [TID]) in adolescent and adult male subjects with FXS. The 12-week, randomized, double-blind, parallel-group, proof-of-concept study design will inform OV101 clinical development and the design of future studies in FXS.

Objectives:

Primary Objectives:

- To evaluate the safety and tolerability of OV101 over 12 weeks of treatment across different daily dosing regimens in adolescent and adult male subjects with FXS

Secondary Objectives:

- To evaluate changes in behavior during 12 weeks of treatment with OV101 across different daily dosing regimens in adolescent and adult male subjects with FXS

Exploratory Objectives:

- To evaluate changes in sleep, adaptive functioning, and quality of life across different daily dosing regimens of OV101 treatment over 12 weeks in adolescent and adult male subjects with FXS
- [REDACTED]
- [REDACTED]
- [REDACTED]
- [REDACTED]
- To explore the relationships among study endpoints (eg, behavior, sleep), where appropriate
- [REDACTED]

Study Population:

Inclusion criteria:

1. Is male and 13 to 22 years old (inclusive) at the time of informed consent.
2. Has a diagnosis of FXS with a confirmed *FMR1* full mutation (≥ 200 CGG repeats). The diagnosis must be confirmed by genetic testing prior to subject randomization.
3. Has a Clinical Global Impression-Severity score of 4 (moderately ill) or greater at screening.
4. Is currently being treated with no more than 3 anti-epileptic and/or psychoactive medications, including those prescribed off-label to address behavioral conditions. Any concomitant medication, including anti-epileptic and/or behavioral medications, supplements, and special diets, must be at a stable dose for at least 4 weeks before randomization and must be maintained at that dose throughout the duration of the study.

5. Has a legally acceptable representative (LAR)/caregiver capable of providing informed consent and able to attend all scheduled study visits, oversee the administration of study drug, and provide feedback regarding the subject's behavior and other symptoms as described in the protocol.
6. Provide assent to the protocol (to the extent possible and in accordance with local institutional review board and regulatory requirements) and have an LAR/caregiver who will provide written informed consent. Subjects providing assent must do so at the same visit as LAR/caregiver written informed consent is provided.
7. Is able to attend all scheduled study visits and willing and capable of performing the required study assessments.
8. Is able to ingest the study drug capsules (including sprinkling capsule contents onto 1 spoon of applesauce or low-fat yogurt).
9. Has an intelligence quotient less than 75 as measured by the Stanford-Binet-5 at screening or a previously documented SB-5 measurement conducted within 6 months of the screening visit. For the site in Israel, please see Appendix for site-specific details regarding the IQ test.
10. Will agree to remain sexually abstinent from the first day of screening until 30 days after the last dose of study treatment.
11. Has LAR/caregivers who will agree not to post any of the subject's personal medical data related to the study or information related to the study on any website or social media site (eg, Facebook and Twitter) until they have been notified that the study is completed.

Exclusion criteria:

1. Has a concomitant disease (eg, gastrointestinal, renal, hepatic, endocrine, respiratory, or cardiovascular system disease) or condition or any clinically significant finding at screening that could interfere with the conduct of the study or that would pose an unacceptable risk to the subject in this study.
2. Has clinically significant lab abnormalities or vital signs at the time of screening (eg, alanine aminotransferase or aspartate aminotransferase $>2.5 \times$ upper limit of normal; total bilirubin or creatinine $>1.5 \times$ upper limit of normal). Re-testing of safety labs may be allowed after consultation with the medical monitor or designee.
3. Uses any GABAergic agent (eg, acamprosate, baclofen, vigabatrin, tiagabine, riluzole, benzodiazepines, and gabapentin) when used on a regular schedule. Benzodiazepines administered for situational anxiety (eg, for occasional procedures or events) are permitted.
4. Uses any cannabinoid derivatives.
5. Has a history of uncontrollable seizure disorder or seizure episodes within 6 months of screening or change in the anticonvulsant pharmacotherapy in the past 3 months.
6. Has a history of suicidal behavior or considered by the investigator to be at high risk of suicide.
7. Has any condition or there is any reason that, in the opinion of the investigator, makes

the subject unsuitable for enrollment

8. Is unable or does not have an LAR/caregiver able to comply with study requirements.
9. Has enrolled in any clinical trial or used of any investigational agent, device, and/or investigational procedure within the 30 days before screening or does so concurrently with this study.
10. Is a family member of the investigator or study site personnel.

Study Design:

This is a Phase 2a, randomized, double-blind, parallel-group study to evaluate the safety, tolerability, and efficacy of OV101 at 3 daily doses: 5 mg/day (5 mg QD), 10 mg/day (5 mg BID), and 15 mg/day (5 mg TID) in adolescent and adult male subjects with FXS. Subjects with a clinically and molecularly confirmed diagnosis of FXS will be eligible for inclusion in the study. The study will comprise a screening period of at least 1 week (to allow for actigraphs) and up to 3 weeks; a baseline visit on Day 1 for treatment randomization (enrollment), baseline assessments, and first dose of study drug; clinic visits for safety and efficacy assessments over a 12-week treatment period, including clinic visits at Week 2, Week 6, and Week 12 (end-of-treatment [EOT]); and an end-of-study (EOS) follow-up visit occurring any time between the ends of Week 16 and Week 18.

For each subject, after informed consent is obtained, screening assessments will be completed within the 3 weeks preceding Baseline. At Baseline, subjects 13 to 22 years old (inclusive) who meet all eligibility criteria will be enrolled on Day 1 in a 1:1 target ratio between adolescents (13 to 17 years old, inclusive) and adults (18 to 22 years old, inclusive). A sufficient number of subjects will be enrolled to ensure that at least 30 evaluable subjects complete 12 weeks of treatment.

Subjects will be randomly assigned in a 1:1:1 ratio to 1 of 3 treatment groups (5 mg QD, 5 mg BID, and 5 mg TID), stratified by age group (adolescent/adult) to achieve balance among treatment arms. All subjects will take study drug TID (morning, afternoon, and evening), OV101 in the morning and OV101 or placebo in the afternoon and evening throughout the treatment period (including Baseline). There will not be any dose adjustments permitted during the study.

After random assignment at Baseline, subjects will receive the assigned package of blinded study treatment according to the treatment code for the first 6 weeks of treatment and will take their first dose of study drug at the clinic. They will receive another assigned package of study treatment at the Week 6 clinic visit.

Subjects (assisted by LAR/caregivers) will complete paper sleep diaries and wear actigraphs over the 7-day periods immediately preceding Baseline and the Week 2, Week 6, EOT, and EOS clinic visits. The Baseline, Week 2, Week 6, and EOT visits will be full-day clinic visits. Safety information will be collected during phone calls at the end of Weeks 1, 4, 8, and 10 (on Days 8, 29, 57, and 71, respectively), in addition to during every clinic visit (screening, Day 1, Week 2, Week 6, EOT, and EOS). At the investigator's discretion, subjects may be evaluated at unscheduled clinic visits for reasons related to subject safety. At unscheduled visits, subjects will be queried about AEs, changes in concomitant medications, and

[figure not shown]
suicidality, and safety laboratory assessments may be conducted. Periodic interim blinded review of safety data will be performed as part of routine pharmacovigilance activities.

Estimated Study Duration:

After informed consent is obtained, screening assessments will be conducted within the 3 weeks preceding Baseline, followed immediately by treatment for 12 weeks and a 4- to 6-week follow-up period, for a maximum duration of individual subject participation of 21 weeks.

Efficacy Assessments:

Efficacy assessments will include the Aberrant Behavior Checklist–Community; the Anxiety, Depression, and Mood Scales; the Repetitive Behavior Scale–Revised; the Conners^{3rd} Edition; the Short Sensory Profile–2; the Pediatric Sleep Clinical Global Impressions (Severity and Improvement) scales; Children’s Sleep Habits Questionnaire; a 7-day sleep diary; the Behavior Assessment System for Children, 3rd Edition Parenting Relationship Questionnaire; Parent Global Impressions (Severity and Improvement) scales; the Pediatric Quality of Life Inventory; a top 3 concerns visual analog scale; the Vineland Adaptive Behavior Scale–3rd Edition; Clinical Global Impressions (Severity and Improvement) scales; 7-day actigraphy; a computerized measurement of cognition using the Test of Attentional Performance for Children; the Repeatable Battery for the Assessment of Neuropsychological Status; [REDACTED]

Safety Assessments:

All subjects who receive study drug will be evaluated for study drug safety and tolerability. Assessments will include: frequency and severity of treatment-emergent adverse events (TEAEs) and serious adverse events (including TEAEs leading to discontinuation), standardized clinical assessment of suicidality, clinical laboratory evaluations, and vital sign measurements.

Study Drug, Dosage, and Route of Administration:

Subjects will be assigned to receive 1 of 3 daily doses of OV101: 5 mg/day, 10 mg/day, or 15 mg/day. Subjects will take all doses orally (assisted by an LAR/caregiver, if necessary), TID (morning, afternoon, evening) at approximately the same times each day, for the duration of the 12-week treatment period.

OV101 Treatment Group	Morning Dose	Afternoon Dose	Evening Dose
5 mg/day	5-mg OV101 capsule	Placebo capsule	Placebo capsule
10 mg/day	5-mg OV101 capsule	Placebo capsule	5-mg OV101 capsule
15 mg/day	5-mg OV101 capsule	5-mg OV101 capsule	5-mg OV101 capsule

The morning and afternoon doses should be taken with food, and the afternoon dose should be taken at least 6 hours after the morning dose. The evening dose should be taken 30 minutes before bedtime. Capsules may be opened and the contents sprinkled onto 1 teaspoon of low-fat semi-liquid food (eg, applesauce, yogurt, pudding) for ingestion, but this approach must be followed consistently throughout the study. The capsule contents must not be placed directly in liquid. The LAR/caregiver must document specifically how each capsule was taken (eg, swallowed whole or taken in 1 teaspoon of food).

Placebo capsules will be identical in appearance to the capsules containing OV101 and have the same excipient ingredients but will not contain OV101. Study drug will be supplied as 5-mg capsules of OV101 and matching placebo capsules in bottles. Bottles will have “Morning,” “Afternoon,” or “Evening” printed on their labels. Each LAR/caregiver will receive a 6-week supply of capsules in a package containing 1 “Morning” bottle, 1 “Afternoon” bottle, and 1 “Evening” bottle at the baseline (Day 1) visit and at the Week 6 visit.

Sample Size:

A sufficient number of subjects (36 estimated) will be enrolled to ensure that 30 evaluable subjects complete 12 weeks of treatment. Subjects will be randomly assigned to the 3 OV101 total daily dosing regimens in a 1:1:1 ratio.

The main emphasis in reporting the data will be on descriptive statistics and estimation with 95% CIs. For the objective of estimating the overall subject incidence of TEAEs (for the 3 OV101 total daily dose arms combined), a true incidence of 20% would be estimated with a 13.9% precision (half-width of the 2-sided 95% CI assuming N = 30).

Analysis Sets:

The randomized analysis set will be used for summaries of subject disposition, demographics, and other baseline characteristics. The safety analysis set (all subjects who receive at least 1 dose of study drug) will be used for the analysis of all safety parameters, analyzed according to treatment received. The full analysis set (all subjects who receive at least 1 dose of study drug and have at least 1 postbaseline efficacy evaluation) will be used for analysis of all efficacy parameters, analyzed according to randomized treatment. The modified full analysis set may be used for exploratory modelling of selected efficacy variables, in addition to the full analysis set.

Statistical Methods:

Descriptive statistics (number of subjects, mean, SD, median, minimum, and maximum) will be presented for continuous variables and their changes from baseline. In addition, 95% CIs for the mean change from baseline will be provided for continuous variables. Graphical displays will be utilized to investigate trends over time and dose and the relationship between

[figure not shown]
certain variables and differences between age groups.

Ordinal variables with sufficient numerical categories (eg, 7-point scales of Parent Global Impressions-Severity and Clinical Global Impressions-Severity) and subscale total scores from questionnaires will be treated as continuous variables.

Categorical (not treated as continuous) endpoints (including adverse event incidence and binary endpoints) will be summarized by frequency and percentage. Frequencies and percentages will be presented for the shifts in these categories (eg, low to normal, low to high, high to low) from baseline to each post-treatment assessment time point for scales with categorical variables. If there are missing values, the number missing will be presented (as a category), but without a percentage. All data collected will be included in by-subject data listings.

All adverse events will be coded using Medical Dictionary for Regulatory Activities (MedDRA) and will be classified by MedDRA system organ class (SOC) and preferred term (PT). The number and percentage of subjects who experience at least 1 TEAE and the number and percentage of subjects who experience at least 1 TEAE within each specific SOC and PT will be presented by daily dosing regimen and overall. The number of TEAEs (event incidence) will also be summarized within each SOC and PT. The Wilson 95% CIs will be displayed for the proportion of subjects experiencing TEAEs as a total across the 3 dosing regimens.

Descriptive statistics for efficacy variables at each time point will be displayed by daily dosing regimen and overall. Post-hoc exploratory modelling may be conducted on selected variables using the full analysis set (and modified full analysis set, as required).

Version and Date of Protocol:

Version 1.2, 27 March 2019

List of Abbreviations

Abbreviation	Definition
ABC-C	Aberrant Behavior Checklist-Community
ADAMS	Anxiety, Depression, and Mood Scales
AE	adverse event
AS	Angelman syndrome
BASC-3 PRQ	Behavior Assessment System for Children, 3 rd Edition, Parenting Relationship Questionnaire
BID	twice a day
CFR	Code of Federal Regulations
CGG	cytosine-guanine-guanine
CGI	Clinical Global Impressions
CGI-I	Clinical Global Impressions-Improvement
CGI-S	Clinical Global Impressions-Severity
Conners 3	Conners 3 rd Edition
CSHQ	Children's Sleep Habits Questionnaire
CSR	clinical study report
DSM-5	Diagnostic and Statistical Manual of Mental Disorders
eCRF	electronic case report form
EDC	electronic data capture
EOS	end of study
EOT	end of treatment
FAS	full-analysis set
FDA	US Food and Drug Administration
FMRP	fragile X mental retardation protein
FXS	fragile X syndrome
GABA	gamma-aminobutyric acid
GCP	Good Clinical Practice
ICF	informed consent form
ICH	International Council for Harmonisation
IQ	intelligence quotient

Abbreviation	Definition
IRB	institutional review board
IWRS	interactive web response system
KABC	Kaufman Assessment Battery for Children
KiTAP	Test of Attentional Performance for Children
KO	Knockout
LAR	legally acceptable representative
MedDRA	Medical Dictionary for Regulatory Activities
mFAS	modified full-analysis set
MMRM	Mixed Model with Repeated Measures
PD	pharmacodynamic(s)
PedsQL	Pediatric Quality of Life Inventory
PGI-I	Parent Global Impressions-Improvement
PGI-S	Parent Global Impressions-Severity
████████	████████
PT	preferred term
QD	once a day
RBANS	Repeatable Battery for the Assessment of Neuropsychological Status
RBS-R	Repetitive Behavior Scale-Revised
SAE	serious adverse event
SB-5	Stanford-Binet-5
SOC	system organ class
SOL	sleep onset latency
TEAE	treatment-emergent adverse event
TID	3 times a day
TST	total sleep time
VABS-3	Vineland Adaptive Behavior Scale, 3 rd Edition
WASO	wake time after sleep onset
WISC	Wechsler Intelligence Scale for Children
WPPSI	Wechsler Preschool and Primary Scale of Intelligence

1 Introduction

Ovid Therapeutics Inc. (Ovid) is developing OV101 (gaboxadol) for the treatment of rare genetic disorders that are associated with severe developmental and behavioral challenges, such as Angelman syndrome (AS) and Fragile X syndrome (FXS). Gaboxadol was initially developed for the treatment of insomnia by H. Lundbeck A/S and Merck, but its development was discontinued in 2007 for clinical and commercial reasons. Extensive nonclinical and clinical data were generated during the initial stages of development by Lundbeck/Merck, including data from exposure to gaboxadol in more than 4300 adult subjects with insomnia and approximately 500 adult subjects in non-insomnia-related studies. Details of the Lundbeck/Merck program, including both the nonclinical program and the clinical program, are found in the investigator's brochure (Ovid Therapeutics Inc. 2017). Unless otherwise indicated, the source for the information in this introduction is the investigator's brochure.

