4.2 Discontinuation of Subjects From Study Treatment and the Study

Discontinuation of a subject from treatment early (before Week 12) for any reason will initiate procedures for discontinuation of the subject from the study, including EOT and EOS visits (Section 3.1). For subjects for whom study treatment is stopped early (before Week 12), an EOT visit should be conducted within 2 weeks after the last day of study medication. After completing the EOT visit, an EOS visit should be completed within 4 to 6 weeks after completing the EOT visit. The duration of the study is defined for each subject as the date signed written informed consent is provided through the EOS visit.

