6.6.1.3 Eliciting and Documenting Adverse Events

Adverse events will be assessed beginning at enrollment (date of signed informed consent) and up to 30 days after the last dose of study drug, and must be followed until resolution or for 30 days after the subject's last study drug dose, whichever comes first.

Serious AEs that occur more than 30 days after the last dose of study drug need not be reported unless the investigator considers them related to study drug.

At every clinic visit after informed consent and at all phone visits (Table 6-1), subjects will be asked a standard nonleading question to elicit any medically related changes in their well-being. They will also be asked if they have been hospitalized, had any accidents, used any new medications, or changed concomitant medication regimens (both prescription and over-the-counter medications).

In addition to subject observations, AEs identified from any study data (eg, laboratory values, physical examination findings) or identified from the review of other documents (eg, subject diaries) that are relevant to subject safety or considered to be clinically significant, in the medical and scientific judgment of the investigator, will be documented on the AE page in the eCRF.

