- All percentages will be rounded to one decimal place. The number and percentage of responses will be presented in the form xx (xx.x), where the percentage is in the parentheses. In the case the numerator is equal to the denominator, the percentage should be presented as (100) instead of (100.0). For TEAEs, the number, percentage, and event incidence will be presented in the form of xx (xx.x) [E], where E is the number of events;

- All listings will be sorted for presentation in order of randomized treatment group, study center, subject, and date of procedure or event;
- All analysis and summary tables will have the analysis population sample size for each treatment group in the column heading (i.e., number of subjects);
- P-values will be rounded to 4 decimal places. P-values that round to 0.0000 will be presented as “<0.0001” and p-values that round to 1.0000 will be presented as “>0.9999”;
- The day of first dose of study drug, OV101, will be defined as Day 1. For day calculation, if date is before first dose date then day=date - first dose date, if date is after first dose date then day=date - first dose date + 1;
- Listings of all data will identify the age group (adolescent/adult) of each subject.

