9.1. Adverse Events

9.1.1 Incidence of Adverse Events

An AE is defined as any untoward medical occurrence in a subject enrolled into this study regardless of its causal relationship to study drug. Subjects will be instructed to contact the investigator at any time after randomization if any symptoms develop.

A Treatment-Emergent Adverse Event (TEAE) is defined as any event AE not present before exposure to study drug or any event already present that worsens in either intensity or frequency after exposure to study drug and occurred within 30 days of last dose. TEAEs will be reported in tables regardless of seriousness.

For listings, any events after pre-specified range above will be flagged in the outputs.

The subject-incidence and event-incidence of TEAEs, TEAEs leading to study discontinuation, treatment-related TEAEs, serious TEAEs, severity of TEAEs, TEAEs with outcome of death, and seizure TEAEs will be summarized by treatment and overall. For summaries of severe or treatment-related AEs, for a given subject, the highest severity or relationship for a specific PT will be considered. Adverse events with missing start dates will be considered treatment emergent. All AEs will be coded using the most current Medical Dictionary for Drug Regulatory Affairs (MedDRA, version 20.1 or higher) and will be summarized by System Organ Class (SOC) and Preferred Term (PT). For each SOC and PT, a subject will be counted only once for subject-incidence tabulations. In addition, TEAE will be summarized by System Organ Class (SOC), High Level Group Term (HLGT), High Level Term (HLT), and Preferred Term (PT). For each SOC, HLT, and PT, a subject will be counted only once for subject-incidence tabulations. The Wilson 95% CIs will be displayed for the proportion of subjects experiencing TEAEs as a total across the 3 dosing regimens. Additional overall AEs (including non-TEAEs) by PTs will also be provided. Detailed listings of AEs, SAEs, treatment-related AEs, and TEAEs leading to study discontinuation will be provided.

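### TEAE event incidence by regimen is a raw count with no time at risk, so it understates the event rate of a regimen with more early stops

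*Protocol*

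**What the plan says.** - **Measure.** The protocol Synopsis (Statistical Methods) and Protocol 7.8.1 both say: "The number of TEAEs (event incidence) will also be summarized within each SOC and PT". SAP 4 fixes the display: "event incidence will be presented in the form of xx (xx.x) [E], where E is the number of events".
- **By regimen.** That protocol sentence does not mention regimen. SAP 9.1.1 does: its list begins "The subject-incidence and event-incidence of TEAEs" and ends "seizure TEAEs will be summarized by treatment and overall".
- **Window.** SAP 9.1.1 limits a TEAE to an event that began or worsened "after exposure to study drug and occurred within 30 days of last dose". Protocol 6.6.1.3 collects AEs "up to 30 days after the last dose of study drug".
- **Early stopping.** Protocol 4.2 says: "Discontinuation of a subject from treatment early (before Week 12) for any reason will initiate procedures for discontinuation of the subject from the study". Protocol 4.2.1 lets the investigator stop study drug for intolerance, and Protocol 3.1 permits no dose adjustment.
- **Numbers.** Protocol 7.5 and the Synopsis: "A sufficient number of subjects (36 estimated) will be enrolled to ensure that 30 evaluable subjects complete 12 weeks of treatment". Allocation is 1:1:1, so about 12 per regimen.
- **Related outputs.** TEAEs leading to study discontinuation are a primary safety endpoint (Protocol 7.1) and are tabulated by treatment (SAP 9.1.1, 9.1.5). Disposition with reasons is by treatment (SAP 5.1). Duration of exposure is by regimen in Protocol 7.8.6.2.1, but SAP 7.2.1 specifies categories by age group and does not mention regimen.

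**The concern.** The primary objective is safety and tolerability across the regimens over 12 weeks. An event count can be compared between regimens only if they are observed for about the same time. Here the observation window moves with the last dose, and the last dose can depend on how well the regimen is tolerated. A lower [E] could then mean fewer events or fewer days of observation. Neither document plans an event rate, a person-time denominator or a time-to-event summary for AEs that would tell the two apart. Because the SAP does not carry over the protocol's exposure summary by regimen, the reader may not be able to make even a rough correction.

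**Working it through.** **The plan's own figures.** For 6 of 30 with z = 1.96, the Wilson centre is (0.200 + 3.84/60)/(1 + 3.84/30) = 0.234. The half-width is 1.96 × √(0.2 × 0.8/30 + 3.84/3600)/(1 + 3.84/30) = 0.139. That gives 9.5% to 37.3%, as in Table 7-1, and the other four columns also reproduce. Enrolment is 30/(1 − 6/36) = 36. Both rest on pooled subject incidence, not on event counts by regimen.

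**Days at risk.** With a last dose on Day 85, a completer has 85 days on drug (SAP 7.2.1 formula) and 85 + 30 = 115 days in the TEAE window. A subject whose last dose is on Day 14 has 14 and 44.

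**Subject-days per regimen.** Assume 12 subjects, k last dosed on Day 14, all 12 completing in the comparison regimen, and a constant event rate.

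- On drug: 14k + 85(12 − k), against 12 × 85 = 1,020
- With the 30-day window: 44k + 115(12 − k), against 12 × 115 = 1,380
- Shortfall in count = 1 − ratio; rate ratio hidden by equal counts = 1/ratio

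| k of 12 | On-drug days | Shortfall | Hidden ratio | Window days | Shortfall | Hidden ratio |
|---|---|---|---|---|---|---|
| 1 | 949 | 7% | 1.07 | 1,309 | 5% | 1.05 |
| 3 | 807 | 21% | 1.26 | 1,167 | 15% | 1.18 |
| 6 | 594 | 42% | 1.72 | 954 | 31% | 1.45 |

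Later stops matter less. With k = 3 and last dose on Day 42, the figures are 891/1,020 (13% fewer) and 1,251/1,380 (9% fewer). If k is the same in every regimen, the ratio is 1 and there is no distortion.

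**Which k is plausible.** The allowance of 6 in 36 gives no arm, reason or timing. In the earlier 12-week study (Protocol 1.4), 3 subjects on twice-daily dosing stopped for AEs. If the 58 treated were split evenly (an assumption), that is 3/29, or 12 × 3/29 = 1.2 per 12. That arm's total of 25 mg/day exceeds the highest daily dose here.

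**Illustration.** Assume 2 TEAEs per completer, Poisson counts and a true rate ratio of 1.25. With no early stops, 24 against 30 events are expected, and the worse regimen's count is no higher than the better one's with probability 0.23. With k = 3 on Day 14, the worse regimen's expectation falls to 30 × 0.791 = 23.7 (on drug) or 30 × 0.846 = 25.4 (window), and the probability rises to 0.54 or 0.45. With a true ratio of 2, the same stops leave 38.0 or 40.6 against 24 (probability 0.04 or 0.02), so a large difference still shows.

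**What a rate would show.** Using window days, 24/(1,380/7) × 100 = 12.2 and 25.4/(1,167/7) × 100 = 15.2 per 100 subject-weeks. The ratio of 1.25 is recovered.

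**The case against.** The strongest reply is that early stopping is already visible. Discontinuation TEAEs are a primary endpoint shown by treatment, disposition and reasons are shown by treatment, and SAP 4 says openly that E is a number of events. Reporting is descriptive, with no planned test of TEAEs between regimens. This stands. A reader might infer that a poorly tolerated regimen could pass as equally safe, or safer, in the safety report. The documents do not support that, because the distortion is in the [E] column and the neighbouring tables would flag the regimen. They would not, however, correct the counts.

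It is also fair that the larger figures need several early stops concentrated in one regimen, and that the constant rate is an assumption. Protocol 1.4 reports from an earlier adult study that most AEs began within 1 to 2 hours of a dose and resolved after stopping. Onset soon after a dose is not the same as onset in the first weeks, so this only partly supports early clustering. If all events did fall in Days 1-14, a Day 14 stop would lose none, and a single overall rate would overstate that regimen by 1.18-fold (window) or 1.26-fold (on drug).

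A reader might also infer that the subject percentages reverse. They lack time at risk too, but with k = 3 on Day 14, a 1.5-fold rate and the 30-day window, the order is kept: 24.0% against 19.7% when events are rare, and 88.3% against 86.5% at 2 events per completer.

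Finally, rates in 12-subject arms are imprecise. With counts of 24 and 30, the 95% interval for the ratio spans a factor of exp(1.96 × √(1/24 + 1/30)) = 1.7 each way. That is a reason not to require finely divided tables, but not a reason to omit the denominator.

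**Conclusion.** The point holds as a limited one. [E] by regimen is a count without time at risk, and it understates the event rate of a regimen with more early stops. At about the early-stop frequency of the earlier study (1 of 12), the understatement is 5 to 7%, which is negligible beside sampling error. At 3 of 12 it is 15 to 21%, enough to blur a modest dose relationship. At 6 of 12, the extreme in which every allowed loss falls in one regimen, it is 31 to 42%. The lower figure of each pair uses the 30-day window and the higher uses drug days only.

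These sizes assume 12 per regimen, last doses around Day 14, no early stops in the comparison regimen and a constant event rate. The effect vanishes if stops are even and shrinks if events cluster early. Nothing here touches the sample size or the pooled Wilson interval. This is a worthwhile, inexpensive improvement to a descriptive table, not a defect in the primary analysis.

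**What to change.** 1. In SAP 9.1.1, keep n (%) [E] and add two items for each regimen: subject-days at risk, from first dose to the earlier of last dose + 30 days or last contact, and the overall TEAE rate per 100 subject-weeks.
2. Split that rate into an early and a later period, for example Days 1-14 and after, so that early-clustered events are not averaged over the whole window. In the 3-of-12 example, both regimens then have 12 × 14 = 168 early subject-days. The later period has 12 × 101 = 1,212 against 9 × 101 + 3 × 30 = 999.
3. In SAP 7.2.1, present duration of exposure by regimen, as Protocol 7.8.6.2.1 states, and not only by age group.

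The cost is a few table columns from dates already collected, with no change to trial conduct. The downside is imprecision: the rates should be read beside the crude percentages. Finer interval tables and a Kaplan-Meier plot of time to first TEAE are optional. The plot mainly describes the any-TEAE measure, which is less affected because a subject who stops for a TEAE is already counted.
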